It has been shown that dysphagia recovery from a hemispheric stroke is associated with an expansion of the swallowing representation in the *unaffected hemisphere*. A treatment approach that facilitates this reorganization in the unaffected hemisphere can help accelerate recovery. Anodal transcranial direct current stimulation (tDCS) is a non-invasive brain stimulation technique that can modulate neuronal excitability of the swallowing motor cortex, and make it more amenable to plastic changes. While it is safe and effective in improving functions in chronic stroke patients, data about its safety and efficacy in acute stroke phase remains sparse. In our pilot study 5 consecutive daily sessions of anodal tDCS to the unaffected swallowing cortex with swallowing exercises was safe and feasible in the acute-subacute stroke phases and showed promise in improving dysphagia. Further confirmation of its safety in early stroke phases and exploration of alternative, more effective doses is vital as a prelude to its examination in confirmatory trials. Besides such **intervention-related factors**, identification of **subject-specific variables** that influence spontaneous swallowing recovery and/or response to the proposed intervention merit examination as they can improve our understanding about the variability of treatment response between subjects, and lead to more efficient study designs by identifying candidates who are more likely to respond to the proposed intervention. We have recently identified a few subject-specific predictors of swallowing recovery from several candidate variables, as outlined in our Preliminary Data. In addition we will use novel neuroimaging measures to obtain surrogate estimates of injury to cortical pathways that regulate

swallowing, and examine the impact of all such subject-related predictors on the effects of our intervention.

Our specific aims are:

Primary Aim: To determine safety and examine effects of 2 different doses of anodal tDCS versus sham stimulation of the swallowing motor cortex of the undamaged hemisphere, combined concomitantly with swallowing exercises, in patients with dysphagia due to an acute-subacute unilateral hemispheric infarction.

Approach:

- A) We will collect data on the effect of our intervention by:
- i) Analyzing changes in penetration and aspiration between the 2 tDCS and sham groups using by a validated assessment tool, the Penetration and Aspiration Scale (PAS) scores;

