 - ii) Examining effects of differing doses of anodal tDCS versus sham stimulation on several physiological measures of swallowing, derived from videofluoroscopic swallowing studies;
 - iii) Evaluating durability of any observed effects of tDCS on dietary status as determined by changes in Functional Oral Intake Scale (FOIS) score at study onset and 1 month.
- B) We will assess safety by comparing the anticipated and observed incidence of the following major adverse events in each of the 3 groups: seizures, stroke specific mortality, neurological and swallowing deterioration as measured by changes in NIH Stroke Scale (NIHSS), and FOIS and PAS scores, respectively.

Secondary Aim: To investigate the impact of subject-specific predictors of dysphagia recovery on the outcome of our proposed intervention.

Approach: We will examine differences in the effect size of our intervention across different strata of subject specific-predictors extracted from our pilot model as well as corticobulbar tract (CBT)-lesion load (as a surrogate measure of lesion size and location) by performing a subgroup analysis using regression models.

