b) Hyoid, Laryngeal, and Pharyngeal excursion (HLPE): we will measure the actual excursion of these structures and landmarks from their resting point to maximal excursion. Hyoid, laryngeal and pharyngeal excursion are all important and semi-independent movements that close off the airway, shorten the pharynx, and open the upper esophageal sphincter, and thus are important variables to measure.

c) Pharyngeal Delay Time (PDT): will provide a temporal measure of the briskness of the swallow onset. We define PDT as “the time in centiseconds that the bolus is present in the hypopharynx before the swallow is triggered”. PDT will be measured from the time the bolus first passes the intersection of ramus of mandible and base of tongue, until the swallow begins - as seen by the final excursion of the hyoid bone associated with the swallow.

2. Dietary Outcome: Functional Oral Intake Scale [FOIS]: An important consequence of dysphagia is a compromised and altered diet. FOIS is a functional outcome that provides a validated measure of diet level. It has been tested and validated in stroke population and demonstrated to be sensitive to changes in swallowing functions in acute stroke patient. FOIS is an ordinal scale ranging from 1 (worst) to 7 (normal oral diet). It is easy to use and does not require specific training. It will be collected at four time points: 1) prior to initiating tDCS/sham stimulation (same day); 2) after the fifth session of tDCS/sham; 3) after the last session of tDCS/sham stimulation; and 4) by telephone at 1 month after the last stimulation session using a standardized questionnaire.

3.1.3

Protocol for Swallowing Evaluation

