Baseline Comparability: While no substantial differences between treatment groups are anticipated given randomization, we will use summary statistics, graphical techniques such as boxplots, and univariate analyses to compare the baseline characteristics of treatment groups. Pre-treatment values will be compared between the placebo- and tDCS-groups using Analysis of CoVariance (ANCOVA) or the Mantel-Haenszel chi-squared test, as appropriate, to determine if the groups are balanced with respect to baseline characteristics while accounting for stratification by dysphagia severity. This comparison will allow us to identify potential confounders to be included in multivariate analyses.

Analytic plan Primary Aim. Primary analysis will use an intent-to-treat approach; thus all randomized subjects will be used in the primary analysis. For the primary outcome variable (PAS) a linear model will be fitted to the data using PROC MIXED in SAS. The outcome will be a change in mean PAS score. Treatment will be included as a categorical variable. Additionally baseline PAS and other variables that will be identified as confounders will be included as covariates. Adjusted means in the two tDCS groups will be compared to those in

the sham group. To control for multiple testing, we will employ the Hochberg-Benjamini procedure, which will result in positive study result if both null hypothesis are rejected at the 0.05 level or one is rejected at the 0.025 level. Similar analyses will be performed on the FOIS, PCR, HLPE, and PDT outcomes. To assess the durability of the intervention effects, a repeated measures analysis will be used. The outcome will be FOIS score at the onset of the trial and at 1 month. Treatment time and their interactions will be included as categorical variables. Additionally other variables that will be identified as confounders will be included as covariates. Adjusted means at the onset of trial and 1 month in the two tDCS groups will be compared to those in the sham group at each time point. *Safety analyses* will be run on all subjects receiving at least one round of intervention. The incidence rates of adverse events will be described as a whole and by treatment group. Adverse events will be presented with and without regard to causality based on the investigator's judgment. *Interim Analyses* No formal efficacy analysis will be performed. The study will not be stopped for early efficacy or futility.

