Analytic plan for Secondary Aim: To assess the effect size across subject-specific predictors (baseline NIHSS score, dysarthria, CBT-lesion load and intubation), subgroup analyses will be conducted. For such analysis regression models will be employed that include intervention, covariate and covariate by treatment interactions as predictors and PAS scores, PCR, PDT, HLPE as outcomes, to examine the modifying effect of the covariates on the intervention. If a significant interaction is detected, analyses of major efficacy endpoints (PAS scores, PCR, PDT, HLPE) will be performed within each group.

Missing Data: Many longitudinal studies have the potential to suffer from problems with missing data. We anticipate a 35% - 40% attrition rate in this study, which includes drop-out, spontaneous recovery and discharge, based on review of our hospital records over the past 5 years. Based on experience, we do not expect any other serious problems with either the extent or the pattern of missing data but we will explore this issue by employing multiple imputation methods for handling missing data.

Sample Size and Power Calculations: We plan to enroll and randomize 99 subjects; 33 subjects to each of the two active and sham treatment. With the above sample size, after 40% attrition, we estimate that a difference of 1.0 and 1.15 standard deviations between the active and sham treatment in the mean primary outcome measure of the study can be detected with a type I error rate of 2.5% and power 80% and 90%, respectively. In our pilot study the difference we estimated was 1.35 with an approximate standard deviation for the differences in the two groups of 1.2, with a standardized difference of 1.1 standard deviations. Thus we expect to have $\geq 87\%$ power to detect the expected differences in our study. We also anticipate a greater effect size in the high dose group and thus the power to be greater.

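### The secondary aim runs at least 16 interaction tests with no stated level or correction and estimates within-group effects only where one is significant; effects with intervals should be reported for every predictor.

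*Combined protocol and SAP*

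**What the plan says.** The secondary aim in Section 2 is "To investigate the impact of subject-specific predictors of dysphagia recovery on the outcome of our proposed intervention". Section 2 also gives the use to which the answer would be put: to "lead to more efficient study designs by identifying candidates who are more likely to respond to the proposed intervention".

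Section 3.1.6 (Analytic plan for Secondary Aim) names the predictors: "subject-specific predictors (baseline NIHSS score, dysarthria, CBT-lesion load and intubation), subgroup analyses will be conducted". The regression models contain "covariate by treatment interactions as predictors and PAS scores, PCR, PDT, HLPE as outcomes". The follow-up step is conditional: "If a significant interaction is detected, analyses of major efficacy endpoints (PAS scores, PCR, PDT, HLPE) will be performed within each group".

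For these tests the plan gives no significance level, multiplicity rule, ranking of predictors or outcomes, cut-points, or power. The one multiplicity statement, "To control for multiple testing, we will employ the Hochberg-Benjamini procedure", stands in the Primary Aim plan and is worked out there for two null hypotheses, the two dose-versus-sham comparisons. All stated power is for the main effect.

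**The concern.** Two features combine. First, four predictors by four outcomes is a screen of at least 16 tests at an unstated level. Section 3.1.2 says of one outcome, HLPE, that "Hyoid, laryngeal and pharyngeal excursion are all important and semi-independent movements". If the three excursions are analysed separately there are 6 outcomes and 24 tests.

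Second, significance in that screen decides which within-group effects are estimated, and they come from splitting the sample. Groups are self-evident for dysarthria and intubation, but not for NIHSS or CBT-lesion load, where cut-points could be chosen after the data are seen.

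What is at stake is the use of the result. A modifier found here is meant to inform who is recruited or stratified in later trials. A false or inflated one would carry into those designs. The primary analysis is unaffected.

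**Working it through.** **Inputs from Section 3.1.6.** 99 randomised, 33 per arm; 40% attrition (upper end of 35% to 40%), so 33 × 0.6 = 19.8, about 20 per arm and 60 in all; pilot difference 1.35, SD 1.2, so 1.35/1.2 = 1.125 SD (the plan rounds to 1.1).

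**Assumptions, not in the documents.** Interaction tests at two-sided 5%; predictor prevalence 20% to 50%; outcome correlation 0 to 0.8; predictor correlation 0 to 0.5; the interaction sizes shown.

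**1. The plan's own power.** Two-sample t-test, 20 per arm, two-sided 2.5%: 79.3% at 1.0 SD, 89.9% at 1.15 SD, 86.9% at 1.1 SD. The stated 80%, 90% and 87% reproduce. They concern the main effect only.

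**2. False signals with no true modifier.** Independent tests: 1 − 0.95^16 = 56.0%; for 24 tests, 1 − 0.95^24 = 71%. Simulating the 4 × 4 grid of 2-df interaction F tests with 20 per arm gives:

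| Outcome correlation | Predictors uncorrelated | Predictors correlated 0.5 |
|---|---|---|
| 0 | 54.5% | 52.7% |
| 0.5 | 51.1% | 45.0% |
| 0.8 | 40.0% | 34.7% |

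The fair range is about 35% to 56%, with about 16 × 0.05 = 0.8 false signals expected. On PAS alone, four independent tests give 1 − 0.95^4 = 18.5%; allowing for correlated predictors, about 16% to 19%.

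**3. Power for a large modifier of PAS alone.** Let each dose have an effect of 1.35 points in one stratum and 0 in the other. With prevalence q, v = 1/(20q) + 1/(20(1 − q)), and the 2-df test (2 and 54 df) has noncentrality λ = 1.125² × 2/(3v).

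- q = 0.5: v = 0.200, λ = 4.22, power 41.5%
- q = 0.3: v = 0.238, λ = 3.54, power 35.5%
- q = 0.2: v = 0.3125, λ = 2.70, power 27.9%

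**4. Exaggeration on passing.** One dose versus sham at q = 0.5 has 10 patients per cell, so SE = 1.2 × √(4/10) = 0.759. The critical t on 54 df is 2.005, so an estimate must exceed 2.005 × 0.759 = 1.52 points, more than the whole pilot effect. Given a true 1.35, estimates that pass average about 2.05 to 2.07, or 1.5 times the truth. The ratio depends on the assumed size: about 2.4 to 2.9 at 0.55 SD and about 1.0 at 2.2 SD.

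**5. Where the screen does work.** A 2.2 SD modifier of one outcome has 88% to 98% power (prevalence 30% to 50%, one dose or doses pooled). A 1.1 SD modifier acting on all four outcomes at a 50:50 split gives at least one significant test in 58% to 86% of trials.

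**6. Inside a split subgroup.** At 50:50, 10 per arm, 1.125 SD and two-sided 2.5%, dose-versus-sham power is 54%.

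**7. Effect of correction.** Under Hochberg over four predictors, a lone true modifier generally has to reach 0.05/4 = 0.0125. Power in step 3 then falls from 41.5% to as low as 21.9% (q = 0.5), and from 27.9% to 12.6% (q = 0.2).

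**The case against.** A reader might infer that the plan hides the results for predictors that fail the test. The text does not support that. The subgroup plan opens unconditionally, Section 2 promises to examine effect sizes across strata, and only the follow-up within-group analyses depend on significance. Nothing says the interaction coefficients will be withheld. The exaggeration in step 4 therefore affects what is selected and emphasised; it does not show that the other estimates go unreported.

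A reader might also infer that the screen will miss any real modifier, or that it selects mostly on noise. Step 5 contradicts the first. The second depends on how plausible each modifier is beforehand, which the documents do not quantify. Nor is the significance condition the sole cause of cutting continuous predictors, since Section 2 already plans strata; the missing cut-points are the gap.

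Further points for the plan stand. The four predictors are prespecified, most of them from a pilot model. Testing interaction before looking inside subgroups is sound practice. The trial is described as a prelude to confirmatory work, so strict error control for this aim is debatable. At 35% attrition there would be 33 × 0.65 = 21.45 per arm, but power for a 1.1 SD single-dose interaction at 50:50 only moves from 39.7% to 42.5%. Multiple imputation is mentioned and might add a little.

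What remains is that an uncorrected screen with low power for plausible modifiers decides which within-group effects are produced, in groups that are undefined for two of the four predictors.

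**Conclusion.** The point holds in this form. At least 16 interaction tests are planned with no level or correction, and within-group effects are produced only after a significant one. The sizes are about 35% to 56% for at least one false signal over the grid (16% to 19% on PAS alone), 28% to 42% power for a PAS-only modifier as large as the pilot effect, and about 1.5 times exaggeration for a single-dose estimate of that size that passes at 50:50. All rest on the assumed 5% level, about 60 completers, and the stated ranges for prevalence and correlation. This is a low-cost improvement to a secondary aim. It is not a flaw in the primary analysis, and it does not establish that a formal multiplicity correction is required.

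**What to change.** In the Analytic plan for Secondary Aim:

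- Delete the sentence that makes within-group analyses conditional on a significant interaction.
- For every predictor, significant or not, report the interaction estimate and each dose-versus-sham effect on PAS change with 95% CI. Take them from the single interaction model using all patients, at fixed values: present/absent for dysarthria and intubation, lower and upper quartile for NIHSS and CBT-lesion load.
- Name PAS change as the lead outcome for this aim and label the PCR, PDT and HLPE interactions exploratory.
- State the number of interaction tests beside any p-value.

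Hochberg correction over the four predictors is optional. It limits false signals but can cut power for the 1.35-point interaction from about 42% to about 22%.

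The cost is a change of wording and a few more table rows. The intervals will be wide: at 50:50 with 19.8 per arm, a single-dose interaction has a half-width of 1.96 × 1.2 × √(8/19.8) = 1.5 PAS points. That is the precision the trial has, and showing it for all predictors answers the aim's question about effect size directly.

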4. DSMB MEMBERSHIP

DSMB Members

The DSMB is a multidisciplinary group independent of NIH/NIDCD and the Principal Investigators. It consists of 5 members, including a biostatistician and four individuals with

expertise appropriate to the study at hand. Additional experts may be consulted on an *ad hoc* basis as needed. The duration of membership will span from the initiation of the study through the completion of the study. It is preferred that members have previous experience serving on safety committees; it is required that the committee chairperson have such experience. The Chairperson will be responsible for managing the conduct of the DSMB during the course of the study and for all communications with the NIH/NIDCD and the Principal Investigator.

All DSMB members will agree to maintain confidentiality about the proceedings of the DSMB meetings and related activities. DSMB members will have no involvement in this trial outside their role on the DSMB and will not act as investigators or sub-investigators on the same or related products.

Other Roles

4.1.1. DSMB Management

An independent Data Coordinating Center (DCC) at Boston University will assist the Principal Investigator in providing DSMB members with required documents and data output and distributing meeting minutes. Any communication of DSMB recommendations or conclusions to NIH/NIDCD, if necessary, will be the responsibility of the Principal Investigator.

4.1.2. Data Management

The DCC will be responsible for generating all output required for the DSMB meetings. An independent Biostatistician from the DCC not involved in any other aspect of the study will be responsible for producing the statistical reports and analysis necessary for the DSMB. The independent Biostatistician will participate in all DSMB open meetings and in DSMB closed meetings as requested by the DSMB. The independent Biostatistician will be unblinded as to study participants' treatment assignments as required to fulfill DSMB obligations.

5. CONFLICTS OF INTEREST

DSMB Members

DSMB membership will be restricted to individuals free of conflicts of interest. A conflict of interest is defined as any incentive, financial or otherwise, that may cause a DSMB reviewer to lose his/her objectivity in the review and evaluation of safety or other data provided to the committee, and which therefore compromises the scientific integrity of the study or biases the conclusions reached by the committee. Conflicts may arise out of the financial or other interests of the DSMB member's spouse/partner or dependent children as well.

These conflicts may include, but are not limited to, the following:

- Compensation to the DSMB members where the value of such compensation may be affected by the outcome of the study, or compensation beyond that which is reasonably or normally paid to clinical or statistical consultants;
- A proprietary interest in the study product, including patent, trademark or copyright, as well as licensing arrangements;

- Receipt of unrestricted grants or gifts;
- Consulting arrangements with the Principal Investigator;
- Lecture fees or review stipends provided by the Principal Investigator at greater than fair market value; and
- Reimbursement of travel expenses not related to his/her service on the DSMB.

DSMB members are responsible for advising the Principal Investigator and NIH/NIDCD in writing of any potential conflicts of interest, as well as any changes in their financial interests, throughout the duration of the study and for one year thereafter. The Principal Investigator and NIH/NIDCD shall be responsible for (i) deciding whether any financial interest of a DSMB member has the potential to create an actual or perceived conflict of interest and (ii) providing disclosure to all other DSMB members of any conflicts of interest that the Principal Investigator and NIH/NIDCD determine do not impede objectivity. Members of the DSMB who develop significant potential or perceived conflicts of interest will be asked to resign from the DSMB.

Independent Data Coordinating Center and Independent Biostatistician

Employees of, or contractors to, DCC, as well as the independent Biostatistician, shall be free of conflicts of interest as defined above. These individuals will be responsible for advising the Principal Investigator and NIH/NIDC in writing of any potential conflicts of interest, as well as any changes in their financial interests, throughout the duration of the study and for one year thereafter. The Principal Investigator and NIH/NIDCD shall be responsible for (i) deciding whether any financial interest of any of the above named individuals has the potential to create an actual or perceived conflict of interest and (ii) providing disclosure to all DSMB members of any conflicts of interest that the Principal Investigator and NIH/NIDCD determine do not impede objectivity.

6. RESPONSIBILITIES

Responsibilities of the DSMB

It is the responsibility of the DSMB to provide an independent review and assessment of the accumulating safety data and to further safeguard the interests and safety of the participating subjects. The primary role of the DSMB is to recommend study continuation or cessation after review of safety data including review of, but not limited to: adverse events (AEs), serious adverse events (SAEs), neurological deterioration, and expected or unexpected patient death and cause of death.

The DSMB will be responsible for ensuring the timely review of all safety data generated, and make recommendations to the NIH/NIDCD and Principal Investigator regarding continuation, termination, or modification of the trial. The DSMB will review data related to the conduct of the study (i.e., the quality of the study and its ultimate ability to address the scientific questions of interest). The DSMB will advise the Principal Investigator and NIH/NIDCD of their recommendation that the trial should continue unchanged, be modified, or be terminated due to safety concerns.

